A novel imaging technology to evaluate functional small airways disease (fSAD) has been developed and validated at the University of Michigan. This technology, termed parametric response mapping (PRM), utilizes voxel by voxel comparison of inspiratory and expiratory HRCT images through co-registration to provide quantitative measures of fSAD. This tool has been utilized in patients with a variety of lung diseases including patients with chronic obstructive pulmonary disease (COPD) and lung transplant recipients (7-9). Higher levels of fSAD in lung transplant recipients with CLAD has been associated with decreased survival, and fSAD values have been shown to increase over time compared to transplant patients without chronic rejection (8, 9). We propose to utilize this novel imaging biomarker to track the change in fSAD, as it relates to change in traditional measures of FEV₁ or FVC, in patients with CLAD enrolled in this clinical trial. We have significant experience in longitudinal monitoring of lung function and have been pioneers in describing the natural history of spirometric decline after CLAD onset (10). Imbio Platform systems, a commercial company with quantitative image biomarker algorithms, will be utilized in this study.

Furthermore, this study will employ a novel biological biomarker of fibroproliferation, mesenchymal stromal cells (MSCs), in assessing the effect of pirfenidone on CLAD. Use of this biomarker is based on 10 years of work in our lab demonstrating that MSCs can be isolated from BAL of lung transplant recipients and are biomarkers of BOS (11, 12). The number of MSCs can be quantitated by a colony forming assay and now as a nested PCR based mRNA measure of unique lung-MSC transcription factors Foxf1 (11). The third aim of this study will investigate the effect of pirfenidone on MSC number and phenotype. This will be the first study analyzing novel imaging and MSC biologic markers of fibroproliferation following administration of a therapeutic agent for CLAD.

Schematic of Study Design

Prior to Enrollment

Obtain informed consent. Screen potential subjects by inclusion and exclusion criteria; obtain medical history; HCRT, BAL (optional), vital signs, EKG, spirometry, pregnancy test (if applicable), concomitant medications, Adverse events from time of signing consent.

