4.4 EXCLUSION CRITERIA

- Acute Rejection (AR) diagnosis by biopsy in the 28 days prior to enrollment
- Treatment with pulse steroids, Anti-thymocyte Globulin (ATG), extracorporeal photopheresis (ECP), plasmapheresis, or Immunoglobulin therapy aimed at CLAD within the 28 days prior to enrollment
- If the subject is receiving chronic Azithromycin therapy, the dose must be stable for the 28 days prior to enrollment
- Presence of active pulmonary infection at the time of enrollment as determined by an investigator in consultation with the treating pulmonologist
- Diagnosis of bronchial stenosis either a) requiring stenting, or b) thought to be responsible for the spirometric decline by principal investigator
- Abnormal liver function tests (AST or ALT > 2 x upper limit of normal (ULN), Alkaline phosphatase > 2.5 x ULN, total bilirubin > ULN) or known cirrhosis (>2 times upper limit of normal of AST/ALT/AP)
- Total WBC < 3.0 K/uL
- Moderate to Severe Renal insufficiency (CrCl <15 mL/min calculated by the Cockcroft-Gault equation)

- Use of any medication known to cause significant interactions with pirfenidone (strong CYP1A2 inhibitors such as Fluvoxamine or Enoxacin or inducers)
- Pregnancy or lactation. Women of child-bearing potential will have a pregnancy test at enrollment and must agree to maintain highly effective contraception with two methods of birth control from the date of consent through the end of the study.
- Tobacco use within 6 months
- History of alcohol abuse in the past 1 year as determined by the treating pulmonologist
- Any condition other than CLAD that will likely result in death in the next 1 year
- Any condition in the judgement of the principal investigator that would preclude participation in this study
- EKG with QTc interval > 500 msec at screening
- Listed for repeat lung transplantation

Excluded therapies:

The following therapies are not permitted during the study:

- Investigational therapy, enrollment in another therapeutic clinical trial within 30 days or 5 half-lives of study medication (whichever is longer)
- Fluvoxamine

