5.0 STUDY VISITS

5.1 Screening

Lung transplant recipients at the University of Michigan will be screened by the study team for participation in this trial. If deemed eligible, subjects will be approached regarding study, and the consent form as well as inclusion and exclusion criteria will be reviewed.

Screening Visit (Performed up to 6 weeks prior to baseline visit and initial study drug dosing) The following procedures will be completed at screening:

- Obtain and document informed consent
- Obtain sex, race, ethnicity, date of birth
- Vital signs (height, weight, temperature, blood pressure, heart rate, respiratory rate, pulse oximetry)
- Review medical history, including transplant history
- Review current medications
- Date of spirometric decline (defined as date of first spirometric measurement used to document spirometric decline) and CLAD phenotype
- Review of bronchoscopy results (if performed in the 6 weeks prior to screening visit)
- Blood draw for screening labs
 - AST, ALT, AP, total bilirubin, creatinine

Screening Bronchoscopy

Bronchoscopy is often employed in routine clinical care to evaluate decline in lung function in lung transplant patients. The University of Michigan (UM) has a standing Institutional Review Board (IRB) approved protocol that that allows for use of BAL fluid for research purposes. If clinical bronchoscopy has been performed within 6 weeks of screening, and no clinical indications of new infection are present (as determined by the principal investigator in consult with the treating pulmonologist), we will utilize the MSC results for this study. If bronchoscopy has not been performed, it may be done following screening and before enrollment, as an

optional part of this study. The informed consent document includes opt in/opt out language for bronchoscopy.

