5.2 Baseline Assessment (Visit 1, Week 0)

At the time of baseline, the coordinator will document the following:

- Vital signs (weight, temperature, blood pressure, heart rate, respiratory rate, pulse oximetry)
- Physical exam including general appearance, HEENT, cardiovascular, pulmonary, abdominal, neurologic, dermatologic, and musculoskeletal exams
- Current medications
- Safety blood work for renal and liver evaluation
 - AST, ALT, AP, total bilirubin, creatinine
- Review bronchoscopy results (if performed)
- ECG
- Perform spirometry
- Undergo an HRCT scan with inspiratory and expiratory image acquisition (if HRCT was not done in preceding 6 weeks)
- Serum pregnancy test (if applicable)
- Review adverse events

5.3 Visits 2, 3, 5, 6 (Weeks 4, 8, 16, 20): may be performed at study center or by local lab draw in conjunction with phone visit

- Safety labs to monitor renal and liver function AP, ALT, AST, total bilirubin, creatinine
- Review hospitalizations
- Review medication compliance
- Review concomitant medications
- Review adverse events

5.4 Visit 4 (Week 12):

- Vital Signs (weight, temperature, blood pressure, heart rate, respiratory rate, pulse oximetry)
- Physical exam including general appearance, HEENT, cardiovascular, pulmonary, abdominal, neurologic, dermatologic, and musculoskeletal exams
- Safety blood work for renal and liver evaluation
 - o AP, ALT, AST, total bilirubin, creatinine
- Spirometry
- ECG
- Review hospitalizations
- Review medication adherence
- Review concomitant medications
- Review adverse events
- 5.5 Visit 7 (Week 24):
 - Vital Signs (weight, temperature, blood pressure, heart rate, respiratory rate, pulse oximetry)
 - Physical exam including general appearance, HEENT, cardiovascular, pulmonary, abdominal, neurologic, dermatologic, and musculoskeletal exams Safety blood work for renal and liver evaluation

- o AP, ALT, AST, total bilirubin, creatinine
- Spirometry
- ECG
- HRCT scan
- Review hospitalizations
- Review medication adherence
- Review concomitant medications
- Review adverse events
- Collect unused study medication and return to investigational pharmacy
- Bronchoscopy with consent of patient and primary physician if no contraindication identified

5.6 Visit 8 (Week 28) (Phone visit):

At the 28 week phone visit, the coordinator will:

- Review hospitalizations
- Review adverse events
- Collect vital status

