C Week 28 visit may be performed as a telephone visit

D In women of child-bearing potential

E Immunosuppression drug levels will be collected and managed per standard of care

F LFTs will be monitored monthly

G HRCT may be done between screening visit and enrollment (visit 1)

H Results of BAL, if performed per standard of care, will be utilized as baseline if performed within the 6 weeks prior to baseline visit. Other bronchoscopies are optional.

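### Only one pregnancy test is scheduled, at Visit 1; none is named during the 24 weeks of dosing or before the week-24 HRCT

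*Combined protocol and SAP*

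**What the plan says.** Pregnancy is an exclusion in Section 4.4, which adds: "Women of child-bearing potential will have a pregnancy test at enrollment". The same criterion requires that these women "must agree to maintain highly effective contraception with two methods of birth control from the date of consent through the end of the study". Table 1, footnote G, treats enrollment as Visit 1. Section 5.2 lists the test at that visit ("Serum pregnancy test (if applicable"), and the pregnancy row of Table 1 has one mark, in the Baseline column.

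The visit lists in Sections 5.3 to 5.6 (Visits 2 to 8) name no pregnancy test. The safety bloods at weeks 4, 8, 12, 16, 20 and 24 are liver enzymes, bilirubin and creatinine. Section 5.5 puts a second HRCT at Visit 7, and Section 5.7 asks for it from subjects who have stopped study drug as well.

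Before Visit 1, Section 5.1 allows a screening visit "Performed up to 6 weeks prior to baseline visit and initial study drug dosing". It includes a "Blood draw for screening labs" with no pregnancy assay listed. Footnote G says "HRCT may be done between screening visit and enrollment (visit 1". Section 5.2 asks subjects at baseline to "Undergo an HRCT scan with inspiratory and expiratory image acquisition (if HRCT was not done in preceding 6 weeks". The study schematic in Section 2 lists, among steps before enrollment, "HCRT, BAL (optional), vital signs, EKG, spirometry, pregnancy test (if applicable), concomitant medications", without giving an order.

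Section 11.3.2(e) requires a report, with outcome follow-up, for a pregnancy arising on study drug or in the 30 days after the last dose.

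**The concern.** The protocol treats pregnancy as a reason not to enter the trial and sets up follow-up for pregnancies that occur on drug. After the first dose, however, it schedules no way of finding one. If conception occurs after Visit 1, a subject who follows the schedule exactly could keep taking study drug and have the week-24 CT with the pregnancy unrecognised. The reporting pathway begins only once someone knows of the pregnancy.

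What is at stake is participant safety. The primary endpoint, its analysis and the power are untouched.

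**Working it through.** The plan gives no figure to reproduce. The check is a count of scheduled tests and the intervals between them.

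**Count.** Screening: 0. Visit 1: 1. The six later visits with safety bloods (weeks 4, 8, 12, 16, 20, 24): 0. Week 28 phone visit: 0. Total: 1.

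**Interval to the second HRCT.** Visit 7 is at 24 × 7 = 168 days with a window of ±14 days, so the scan falls 168 − 14 = 154 to 168 + 14 = 182 days after the only test.

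**Interval before Visit 1.** The screening period is at most 6 × 7 = 42 days. This is a ceiling: it needs a study scan on the day of screening and a full six-week wait.

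**What added tests would achieve.** Visit days with the Table 1 windows, taken as counted from Visit 1:

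- Visit 2 (week 4): 28 ± 7 = 21 to 35
- Visit 3 (week 8): 56 ± 7 = 49 to 63
- Visit 4 (week 12): 84 ± 14 = 70 to 98
- Visit 5 (week 16): 112 ± 7 = 105 to 119
- Visit 6 (week 20): 140 ± 7 = 133 to 147
- Visit 7 (week 24): 168 ± 14 = 154 to 182

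The longest gap between two tests at the window limits is the latest day of the later one minus the earliest day of the earlier one.

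| Tests added after Visit 1 | Assays per woman | Longest gap as scheduled (days) | Longest gap at window limits (days) |
|---|---|---|---|
| Visit 7 only | 1 | 168 | 182 |
| Weeks 12 and 24 | 2 | 84 | 182 − 70 = 112 |
| Weeks 8, 16 and 24 | 3 | 56 | 182 − 105 = 77 |
| Every draw, weeks 4 to 24 | 6 | 28 | 98 − 49 = 49 |

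In the last row, 119 − 70 and 182 − 133 also give 49; the other gaps are 35, 63 − 21 = 42 and 147 − 105 = 42.

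**What follows a positive result.** Section 11.3.2(e) sets out reporting and follow-up. Section 8.1 says when to reduce, interrupt or stop treatment for liver tests, rash, gastrointestinal effects and QTc, but does not mention pregnancy. Adding tests without a stated action would leave that step open.

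**The case against.** **Existing controls are substantial.** Two contraceptive methods are required from consent to the end of the study, which also covers week 24 and subjects off drug. Adverse events are reviewed every four weeks, and pregnancies are reported and followed. This stands as a reason to think the risk is low. It does not close the gap: contraception lowers the chance of pregnancy, open questioning depends on the subject already knowing, and reporting starts after recognition.

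**A test may exist elsewhere.** The Table 1 row for standard-of-care labs is not itemised beyond immunosuppressive drug levels. Part of the text after the start of the schematic was not available, nor were the consent pages. This stands as a limit: what is shown is that the Section 5 lists and Table 1, which cover every visit, name no further test.

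**The gap before Visit 1 is thin.** The schematic already lists a pregnancy test before enrollment; only its order relative to the scan is open. Many scans before Visit 1 may be routine care, since Section 2 says they are customary at CLAD onset. Section 5.2 allows such scans to be reused, and a study test cannot govern them. This largely stands. A reader might infer that a pregnancy present at an early study scan would run on unnoticed through dosing to the week-24 CT. The documents do not support that: the Visit 1 test comes with the visit to which first dosing is tied, and pregnancy is an exclusion, so entry would normally stop there.

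**The size of the risk is undocumented.** The documents give no number of women who could become pregnant, no pregnancy rate and no statement of fetal risk from the drug or the scan. This stands, and no expected number of exposed pregnancies can be given.

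**Conclusion.** The point holds for the period after Visit 1. The schedule contains one pregnancy test, followed by 24 weeks of dosing and a CT 154 to 182 days later with no further test named. A pregnancy starting in that time could go undetected through both.

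The period before Visit 1 is a minor second point. A study-ordered HRCT may precede the test by at most 42 days, and the exposure is one CT.

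The conclusion rests on the Section 5 visit lists and Table 1 being the full schedule of study tests, and on visit windows being counted from Visit 1. It does not imply that the plan ignores pregnancy, that any particular number of women would be exposed, or that the trial's results are at risk. It is a safety gap of unknown but probably small frequency, worth closing because the remedy is cheap.

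**What to change.** For women of child-bearing potential:

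1. Require a negative pregnancy test at Visit 7 before the week-24 HRCT, including for subjects who have stopped study drug.
2. Add a pregnancy assay to the existing safety draws at weeks 4, 8, 12, 16 and 20. With the Visit 7 test this brings the longest untested interval after Visit 1 to 28 days as scheduled and 49 at the window limits. A sparser schedule is possible at the longer intervals tabulated above.
3. State the action on a positive result: stop study drug, omit the study HRCT and start the Section 11.3.2(e) reporting.
4. Secondary: require a negative test before any study-ordered HRCT done before Visit 1, and keep the Visit 1 test. Routine-care scans are outside this rule.

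The cost is up to six added assays per woman (five at weeks 4 to 20, one at Visit 7), all on existing draws, plus at most one pre-scan test, which can use the screening draw if the scan is close to it. To give a scale, assume that 5% to 15% of subjects are concerned. The documents give no share, and they give enrollment as 60 (Section 4.2) or 66 (Section 10.2). Then 60 × 0.05 = 3 and 66 × 0.15 = 9.9, or about 3 to 10 women. That means 3 to 10 assays if only Visit 7 is added, 18 to 60 if all six are, and up to 3 to 10 pre-scan tests.

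Local laboratories used at weeks 4, 8, 16 and 20 need the assay on their order, and the Visit 7 result must be available before the scan. No extra visit is needed.

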6. RECRUITMENT

University of Michigan has in place a unique prospectively collected dataset of lung transplant patients (Organ Transplantation Information System (OTIS) database). We have, as a part of this database, devised a system in which every patient's baseline lung function post-transplant is analyzed to generate their baseline FEV1 as well as their CLAD status. The trial's study team will screen lung transplant patients using this program to identify potential subjects.

We have run this profile once to determine if recruitment of 60 CLAD patients is viable in the planned two years. At present among all alive patients with lung transplant at our center, 92 patients meet spirometric criterion for CLAD. Phenotype and grade distribution are shown below:

* CLAD grade is based on ISHLT definition. The study plans to include all patients with diagnosis of CLAD irrespective of the stage. Fibroproliferative remodeling in a transplanted lung is an ongoing event as evidenced by continued progressive decline in lung function, worsening of small airway obstruction, and evidence of change in the phenotype of mesenchymal cells isolated from BAL of these patients. It is important that an anti-fibrotic agent be effective at all stages of CLAD because patients can present in any stage of CLAD at the very disease onset. Furthermore, CLAD becomes a chronic disease and patients can survive for prolonged periods of time after onset of CLAD. Hence, the ability of an antifibrotic agent to halt fibroproliferation at various time points after onset of CLAD is of key significance.

^A CLAD is identified by decline in FEV1 below 80% of post-transplant baseline as per ISHLT definition. Our published work has shown that patients can present either as an isolated decline in FEV1 (BOS) or as a concurrent decline in both FEV1 and FVC, also termed restrictive allograft syndrome (RAS).¹⁰ As both of these presentations arise from fibrosis, we will not limit our study to one specific phenotype.

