2. BACKGROUND/RATIONALE/PRELIMINARY STUDIES

Our principle hypothesis is that pirfenidone therapy will stabilize lung function decline and slow progression of fSAD in lung transplant recipients with CLAD.

Greater than 50% of lung transplant recipients show signs of CLAD by 5 years posttransplantation (1). This process arises from development of graft fibrosis in a peri-bronchial (bronchiolitis obliterans or BO), peri-vascular, or fulminant interstitial and airway luminal fibrosis distribution (2, 3). Therapies to prevent or slow CLAD are lacking. Anti-fibrotic therapies may offer an avenue to prevent progression of CLAD and prolong allograft survival.

Pirfenidone, an oral anti-fibrotic agent, was approved for treatment of idiopathic pulmonary fibrosis (IPF) in 2014. In large multi-center, international clinical trials, pirfenidone has been shown to reduce the rate of FVC decline in patients with IPF with a favorable safety and tolerability profile (4, 5).

Small airways, the predominant histologic target of fibrotic remodeling in a chronically rejecting lung allograft, have been termed the "silent zone" of the lung secondary to difficulty in evaluating this disease process by pathology or imaging (6). While high resolution CT (HRCT) scans are routinely obtained at CLAD onset, HRCT findings in CLAD lack specific diagnostic features, and small airways cannot be visualized or evaluated by standard methods.

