4. EXPERIMENTAL DESIGN

4.1 ENDPOINTS

Primary:

- Change in functional small airways disease (fSAD) as measured by parametric response mapping (PRM) at 24 weeks by treatment arm

Secondary:

- Change in FEV₁ over 24 weeks by treatment arm
- Change in FVC over 24 weeks by treatment arm
- Number of subjects with treatment intolerance over 24 weeks
- Number of subjects with adverse events related to treatment with Pirfenidone

Exploratory:

- Change in bronchoalveolar lavage (BAL) mesenchymal colony forming units (CFUs) by treatment arm
- Change in fibrotic phenotype of BAL mesenchymal cells (expression of collagen, alpha smooth muscle actin, beta-catenin, fibronectin) by treatment arm

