4.3 INCLUSION CRITERIA

- Lung transplant recipients 18 years of age or older.
- Greater than 6 months after single or bilateral lung transplantation
- Baseline FEV₁ and FVC values (mean of two highest value measured 3 weeks apart) > 50% predicted (to assure viable graft)
- Diagnosis of CLAD (two consecutive spirometric values of FEV₁ alone or both FEV₁ and FVC < 80% of baseline)

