5.8 Randomization

This is a randomized, double-blind, placebo-controlled multi-center study. Assignment to study treatment will be blinded to the study subjects, investigational site personnel, study vendors, and the Sponsor study team, except for the delegated personnel who will review and check the randomization and drug allocation for accuracy.

All patients will be randomized at the Baseline visit, using stratified block randomization with undisclosed block sizes. The stratification factor is FEV1 first vs concurrent FEV1 and FVC decline at time of CLAD onset. Our statistician, [name], will assist with randomization. She will provide the Research Pharmacy (via email) with randomization codes for two separate strata as mentioned above. Within each stratum the statistician will indicate treatment assignment"Active Pirfenidone" or "Placebo" and treatment label ID number. The Research Pharmacist (RP) will be told upon patient entry the stratum to which the patient belongs, identifying the appropriate randomization list for each patient. The RP will then dispense Active or Placebo based on the randomization code on the randomization list. The RP will refer to the randomization code at each dispensing.

In the event of a medical emergency in which breaking the blind is required to provide medical care to the subject, the investigator may obtain treatment assignment directly from the study statistician for that subject.

Visit	Screening ^A	1 Baseline	2 ^B +/- 7days	3 ^B +/- 7days	4 +/- 14day	5 ^B +/- 7days	6 ^B +/- 7days	7 EOT +/-	8 EOS +/-
					S			14day s	7days
Week	-6 - 0	0	4	8	12	16	20	24	28 ^c
Inclusion/exclusion criteria	х								
Informed consent	Х								
Randomization		Х							
Demographics	Х								
Vital Signs	Х	Х			Х			х	
Physical exam	Х	Х			Х			х	
Medical history	х	х							
Adverse events	х	х	Х	х	х	х	х	х	х
Non-elective hospitalizations		х	x	x	x	х	х	х	x
Medication Compliance			Х	х	х	х	х	х	
Concomitant medications	X	x	х	x	x	х	x	х	
Pregnancy test ^D		Х							
Standard of care labs	x	x	х	х	х	х	х	х	
including									
immunosuppressive									
drug levels									
Safety labs (LFTs) ^F	Х	Х	Х	Х	Х	Х	Х	Х	
Spirometry	Х				Х				
Full PFTs		Х						Х	
HRCT ^G		Х						Х	
EKG		Х			Х			Х	
Bronchoscopy with BAL ^H	x	x						х	
Vital status assessment									х

Table 1. Schedule of Assessments

A The time period between the screening and enrollment visit may be up to 6 weeks

B Weeks 4, 8, 16, 20: Laboratory testing may be performed locally

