10.2 Sample Size Justification

We will describe the distribution of fSAD change within and between treatment groups (n=30 per group) over a 6-month period. Preliminary data suggests that without treatment, fSAD increases 9% on average over a 6-month time period with SD of 9%. If pirfenidone halves this increase over 6 months, we would have a confidence interval for the treatment effect of 4.5+/-4.64%. Power to detect 6-month treatment differences is sensitive to assumptions of the standard deviation above and the ability of pirfenidone to reduce 6-month fSAD progression; a power analysis table is given below for various effect sizes and standard deviations that might be seen in the trial based on a sample size of 60 (30 per group).

	% Increase in FSAD for Pirfenidone Group (vs 9% FSAD increase in Placebo Group)			
Std Dev	0%	2%	4.5%	
5	>99%	>99%	93%	
7	>99%	97%	69%	
9	97%	84%	48%	

We will similarly summarize changes in spirometric parameters and MSC CFU and phenotype over time between and within groups.

While the above power is shown with 60 patients (30 per group), we will plan to enroll 66 patients (33 per group) to account for subject drop out.

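### Randomisation is stratified by CLAD phenotype, but the analysis of the primary endpoint neither includes the stratum nor reports fSAD by stratum

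*Combined protocol and SAP*

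**What the plan says.** The sole primary endpoint (protocol sections 4.1 and 10.1) is "Change in functional small airways disease (fSAD) as measured by parametric response mapping (PRM) at 24 weeks by treatment arm". Eligibility in section 4.3 admits CLAD defined by "two consecutive spirometric values of FEV₁ alone or both FEV₁ and FVC < 80% of baseline". Footnote A of section 6 labels the isolated form BOS and the concurrent form RAS, and pools them on purpose: "As both of these presentations arise from fibrosis, we will not limit our study to one specific phenotype".

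Section 5.8 then states: "The stratification factor is FEV1 first vs concurrent FEV1 and FVC decline at time of CLAD onset". No other factor is named. Section 5.1 has CLAD phenotype recorded at screening.

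Section 10.2 rests on a single planning figure: "Preliminary data suggests that without treatment, fSAD increases 9% on average over a 6-month time period with SD of 9" percent. It describes fSAD change within and between treatment groups. Section 10.3, headed as the primary endpoint analysis, names no model and does not mention phenotype. The table of contents lists no data-analysis section beyond 10.1 to 10.3.

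**The concern.** Stratifying on phenotype implies that it is expected to matter for outcome. Section 2 gives some reason to ask whether it also matters for this particular endpoint. It describes graft fibrosis as peri-bronchial, peri-vascular or of a "fulminant interstitial and airway luminal fibrosis distribution", while the primary measure is one of functional small airways disease. A shared fibrotic origin is a reason to enrol both forms. It does not by itself show that fSAD changes equally in both.

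If the pooled difference is small or null, the team will want to know whether that holds in both phenotypes. The plan offers no prespecified answer. A by-stratum table made after a disappointing result would still compare randomised groups within strata, but it would be open to the charge of selective reporting. In a phase II trial that seeks a radiographic signal, the phenotype in which the signal appears bears on the next study.

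There is a second, smaller point. If the stratum predicts fSAD change, an analysis that ignores it tends to overstate the standard error of the treatment difference.

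**Working it through.** **1. Is the stratum used anywhere?** Set side by side, section 5.8 defines two strata, section 5.1 collects the phenotype, and sections 10.1 to 10.3 describe fSAD by arm only. They contain no stratum term, no interaction and no stratum estimate.

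**2. The plan's own figures reproduce.** Inputs from section 10.2: 30 per arm; placebo increase 9; pirfenidone increase 0, 2 or 4.5; SD 5, 7 or 9. Alpha is not stated; two-sided 5% is assumed. Two-sample t-test power (58 df):

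| SD | difference 9 | difference 7 | difference 4.5 |
|---|---|---|---|
| 5 | >99.9% | >99.9% | 92.9% |
| 7 | 99.8% | 96.8% | 68.7% |
| 9 | 96.8% | 84.2% | 47.8% |

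All nine cells agree with the plan. The interval half-width is t(58) × 9 × √(2/30) = 4.65, against 4.64 stated. There is no arithmetic error. The table simply assumes one common effect.

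**3. Precision of the missing estimates.** The concurrent share cannot be read in the supplied text, because the distribution in section 6 did not survive extraction. That is not a fault of the plan. A range of 10 to 40% is assumed, with 60 patients analysed and equal arms within strata.

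- Stratum half-width = t(2m − 2) × SD × √(2/m), where m is the number per arm in the stratum.
- Interaction half-width = t(56) × SD × √(2/m₁ + 2/m₂).

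Example at a 20% share and SD 9 (24 and 6 per arm):
- FEV1-first: 2.013 × 9 × √(2/24) = 5.23
- Concurrent: 2.228 × 9 × √(2/6) = 11.58
- Interaction: 2.003 × 9 × √(2/24 + 2/6) = 11.64

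| Concurrent share | per arm (FEV1-first / concurrent) | FEV1-first | Concurrent | Interaction |
|---|---|---|---|---|
| 10% | 27 / 3 | 4.92 | 20.40 | 15.52 |
| 20% | 24 / 6 | 5.23 | 11.58 | 11.64 |
| 30% | 21 / 9 | 5.61 | 8.99 | 10.16 |
| 40% | 18 / 12 | 6.10 | 7.62 | 9.50 |

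(95% half-widths in fSAD points, SD 9.) Section 10.3 expects a lower SD. At SD 5 the ranges are 2.7 to 3.4 for FEV1-first and 4.2 to 11.3 for concurrent decline.

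**4. Power of the interaction at SD 9.** For a true difference between strata of 4.5 points it is about 8 to 15%; for 9 points, about 21 to 46%. A test of interaction would therefore settle little.

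**5. Does pooling dilute the effect?** Suppose concurrent patients show no fSAD progression, their share is q in the preliminary data and p in the trial, and 9 is the preliminary mean. FEV1-first patients then progress by 9/(1 − q). Halving that gives a pooled trial difference of 4.5 × (1 − p)/(1 − q).
- If q = p, the difference is 4.5 at every share, and power at SD 9 stays at the plan's 48%.
- If q = 0, it is 4.5 × (1 − p), or 4.05 to 2.70 for p = 10 to 40%.

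The documents give neither q nor any fSAD change by phenotype, so the size of any dilution cannot be fixed.

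**The case against.** The other side has a strong case, and most of it stands.

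- **The pooled estimate is sound.** The stated target is CLAD of either form, pooling is deliberate, and the randomised contrast estimates the average effect in that population. A reader might infer that a null pooled result could not be interpreted. The documents do not support that. FEV1 and FVC are secondary endpoints, BAL mesenchymal markers are exploratory, and stratified randomisation keeps a by-stratum comparison valid.
- **Insensitivity of fSAD in concurrent decline is not documented.** No section says so. Section 2 calls small airways "Small airways, the predominant histologic target of fibrotic remodeling in a chronically rejecting lung allograft" with no exception by phenotype. The interstitial form it lists also includes airway luminal fibrosis, and concurrent-decline patients have lost FEV1 as well.
- **A specific loss of power cannot be claimed.** A reader might infer that power in the halving case at SD 9 falls from 48% to between 40% and 21%. That needs q = 0, meaning that the 9% describes FEV1-first patients only. If the 9% already averages the same mix, nothing is lost.
- **A rule that confines the conclusion to one phenotype when placebo fSAD does not progress in the other would be unsafe.** It has no natural threshold and would rest on about 3 to 12 placebo patients. The 95% half-width of their mean at SD 9 runs from about 22 to 6 points.
- **Stratifying for balance does not oblige a subgroup analysis in 60 patients.** This is true, and it is why the estimates should be descriptive.

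None of this gives a reason to leave the stratum out of the model or to leave the by-stratum table unplanned.

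**Conclusion.** The gap is real, modest and cheap to close. The plan randomises within phenotype strata and then sets the strata aside when analysing its only primary endpoint. The average effect remains validly estimated. What is lost is a prespecified view of whether a null or small fSAD result is uniform or differs by phenotype.

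The size of the problem cannot be stated as lost power. What can be sized is the remedy. With 60 analysed, SD 9 and an assumed 10 to 40% concurrent share, the FEV1-first difference is estimated to within about 4.9 to 6.1 points, close to the pooled 4.65. The concurrent difference is known only to within 7.6 to 20.4 points. At shares of 10 or 20% that is wider than the whole 9-point planning increase. The by-stratum results would reduce the ambiguity without removing it.

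**What to change.** Add to section 10.3:

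> The primary fSAD model will include the randomisation stratum, and the pooled estimate remains primary. Treatment differences with 95% CI, the treatment-by-stratum term and the placebo-arm fSAD change will also be reported by stratum as descriptive analyses.

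Section 10.3 names no model at present, so this text needs one to attach to. A linear model of fSAD change on arm and stratum is the simplest one consistent with the t-test behind the power table. It would also help to state in section 10.2 the phenotype mix of the preliminary data, if known.

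Cost: one covariate, one interaction term and one table, on data already collected, with no extra patients or visits. The downside is imprecision, especially in the concurrent stratum, so the text should say that these results are supportive only. The change should be made before treatment codes are opened; after that, the same table would have to be labelled post hoc.
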